1.2 Study Rationale

COVID-19 demonstrated the potential of pandemics to overwhelm local and state medical infrastructures to diagnose and treat patients, while attempting to minimize further transmission risks to the un-infected. Furthermore, the COVID-19 pandemic has impacted the conduct of clinical trials of medical products, leading to challenges in meeting protocol-specified procedures, including adhering to protocol-mandated visits and laboratory/diagnostic testing. Overall, the emergence of DCTs may help improve trial participant engagement, recruitment, enrollment, and retention of a meaningfully diverse clinical population.

Enabling technologies that would enable the collection of blood and other diagnostic samples at the point-of-care by the patient/participant while at a remote location could potentially offer several benefits, eg, improved patient/participant convenience and comfort, early diagnostic sampling (and thereby potentially early diagnosis), greater participant study compliance (especially for pharmacokinetic and biomarker research endpoints), relief of phlebotomy-related bottlenecks while reducing any potential transmission risks.

Advancing technologies that can enable blood collections by the patient or study participant while remaining at a remote location provide a potentially attractive alternative for patients who are not critically ill. These technologies have the potential to minimize transmission-risk and accelerate the timeline for diagnosis and treatment. Furthermore, this would allow for the better channeling of potentially limited medical resources (eg, phlebotomists, HCP) toward managing a pandemic response. In a clinical trials' setting, this may be more attractive to study participants, sparing them the need for frequent clinic visits, and would reduce the overall costs associated with frequent clinic visits.

Enabling such self-collection devices has the potential to take the initial evaluation of a patient closer to the point-of-care, supporting telemedicine strategies and virtual clinical trials. Advancing such innovative technologies requires that device performance and user experience be compared to the current standard of care offered by in-clinic HCPs.

Examples of Tasso device use for SARS-CoV-2 antibody testing have been published in the literature. In one study, the use of Tasso device for capillary blood self-collection was associated with a high success rate (93.4% of participants in unsupervised settings and 94.5% of participants in supervised settings) and an excellent concordance (overall accuracy of 98.9%) for anti-SARS-CoV-2 IgG results when compared to standard venous blood-derived sera ([Hendelman et al., 2021](#)). In another study, 70.0% of participants were able to collect an adequate sample for testing using the Tasso device. Among those with an adequate sample, there was a high concordance in results between the Tasso/SST and phlebotomy blood collection methods (Cohen's kappa coefficient = 0.88). Moreover, the

Tasso device receives a high-level (90.0%) of acceptance among all participants ([Wixted et al., 2022](#)). To note, the higher failure rate (30.0%) observed by [Wixted et al., \(2022\)](#) compared to the failure rate of 6.6% observed by [Hendelman et al., \(2021\)](#) could be due to an older population (median age and range of 58.0 years [45.0 to 68.0 years] vs 45 years [21 to 73 years]), in which manual dexterity or comorbidities could be more likely to affect use of the device.

The Tasso+™ lancet is an enabling technology that is an FDA 510(k)-cleared Class II medical device that aims to improve upon the traditional venipuncture blood collection experience. This study aims to evaluate the third generation Tasso+™ device with Tasso+™/SST and Tasso+™/EDTA collection kits with respect to device performance and user experience in adult participants who are healthy or in well-compensated health. The Tasso+™/SST collection kit will be used to evaluate serum while the Tasso+™/EDTA collection kit will be used to evaluate whole anticoagulated blood and plasma.

The laboratory results of Tasso+™/SST capillary collection tube will be compared on Day 1 to blood collected using the standard venipuncture by an HCP across an array of laboratory tests being tested by laboratory technicians at a single central laboratory ([Table 4](#)).

Establishing correlation coefficients of laboratory results collected by a study participant and compared to standard venipuncture will be an important milestone to rely solely on the patient/study participant to self-collect blood using either device/kit collected and to ship the samples to a designated laboratory. Indeed, in a recent study, even though Tasso/SST serum protein measurements were highly reproducible, self-collection at home with delayed sample processing was associated with significant concentration differences for several analytes compared to supervised, in-clinic collection with rapid processing ([Brandsma et al., 2022](#)). These results are to be compared to higher concordance results obtained among other studies focusing on serology: overall accuracy of 98.9% in the study conducted by [Hendelman et al., \(2021\)](#) and Cohen's kappa coefficient of 0.88 in the study conducted by [Wixted et al., \(2022\)](#).

The sample integrity of Tasso+™/SST (ie, adequate volume and absence of moderate or gross hemolysis) and Tasso+™/EDTA (ie, adequate volume, absence of moderate or gross hemolysis, and absence of clotting) capillary collection tubes will be evaluated on Day 1 for each cohort and on each of Days 29 and 57 for Cohorts A and B combined ([Table 4](#)).

Table 4 Sample Testing Table

Method of blood collection	Laboratory Results		Sample Integrity		
	SARS-CoV-2	Chemistry*	Sample Volume	Hemolytic Index	Clotting
Tasso+™ device	EDTA	✓	✓	✓	✓
	SST	✓	✓	✓	✓
Venipuncture	EDTA	✓			
	SST	✓	✓		

EDTA=ethylenediaminetetraacetic acid; SST=serum separator tube

Footnotes: Chemistry analytes include sodium, potassium, chloride, blood urea nitrogen, creatinine, glucose, phosphate, uric acid, and C-reactive protein.

There will be no complete blood count laboratory analysis using Tasso+™/EDTA capillary collection tube due to potential for red cell lysis and clotting, and insufficient blood volume collection that may preclude accurate results.

The impact of the timing of centrifugation after blood collection with Tasso+™ on blood sample integrity and accuracy will be evaluated on Day 1, as Tasso+™ blood samples of Cohort A participants will be centrifuged after shipping to the Central Laboratory, while Tasso+™ blood samples of Cohort B participants will be centrifuged and aliquoted by the Site prior to being shipped to the Central Laboratory alongside with venipuncture blood samples that will be centrifuged prior to shipping as per standard procedures.

Subsequent Tasso+™ administrations will be conducted remotely by the study participant to further document the device performance and user experience. Participants will receive proctor-support from the Site on Day 29 (and if requested, on Day 57). The results of this study may provide data to ensure the feasibility of decentralized, blood collections, thus supporting telemedicine strategies and virtual clinical trials.

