4 STUDY PLAN

4.1 Overall Study Design and Plan

This is a Phase 1, multicenter, observational study that will evaluate the Tasso+™ device in approximately 200 male or female adult participants in an outpatient setting who are healthy or in well-compensated health at up to 5 US sites.

The Investigator will obtain electronically signed informed consent (eConsent form) from the participant before any study procedures are performed. For further details regarding the informed consent process, see [Section 11.3](#).

Each participant will be followed with a study visit in the Clinic on Day 1, and subsequent decentralized, remote study visits on Days 29, 57, and 85. The total duration of study participation is expected to be 85 ± 3 days.

On Day 1, each participant will be randomized 2:1 to either Cohort A or Cohort B. Tasso+™ blood samples of participants randomized to Cohort A will be shipped to the Central Laboratory where they will be centrifuged and aliquoted. However, Tasso+™ blood samples of participants randomized to Cohort B will be centrifuged and aliquoted at the Site prior to shipping to the Central Laboratory, following the same approach used for venipuncture blood samples.

The decentralized visit on Day 29 (Visit 2) will be remotely supported by a prescheduled proctor during working hours to support the participant's self-administration of the Tasso+™ device. For the decentralized visit on Day 57 (Visit 3), the participant will have the option to request a prescheduled proctor session during working hours to support the participant's self-administration of the Tasso+™ device.

The participant will use an electronic diary (eDiary) to report symptoms for 28 days following each Tasso+™ device administration (Symptom questionnaire) and to report on the usability of the Tasso+™ device (Tasso questionnaire) immediately following each Tasso+™ device administration (on Days 1, 29 and 57) and on Day 85. Contact information will be provided to each participant in the event they have concerns or they need help during working hours while using the Tasso+™ device.

Venous blood collection (phlebotomy) will take place on Day 1; capillary blood collections using Tasso+™ device will take place on Days 1, 29, and 57; usability data will be collected after each use of Tasso+™ device and on Day 85; reliability of the device will be collected after each use of Tasso+™ device (Days 1, 29, and 57).

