4.2 Steps to the Process

4.2.1 *Training*

Training will be provided on Days 1 and 29 and will include detailed IFU and online video training. The detailed IFU will be provided in a separate document, and an overview of IFU is provided in [Section 7.4](#). When administering the Tasso+™ remotely, participants will receive proctor-support from the Site on Day 29 (and as requested, on Day 57) during working hours, the intent being to guide the participant through the process and to help troubleshoot should any difficulties be encountered. Training on Day 57 should be performed only if it is specifically requested due to participant hesitation.

4.2.2 *Blood Collection*

Once trained, and by following the IFU provided (see [Section 7.4](#)), participants will self-administer the Tasso+™ device in the Clinic at the Investigator site (supervised) and subsequently remotely, ie, at home or a suitable remote location (proctor-supported on Day 29 and unsupported on Day 57). Self-collection may be additionally supported on Day 57 using a proctor session, as requested, to guide the participant through the process and help to troubleshoot any difficulties. The SST tube will be preferably collected from the left upper arm and the EDTA tube will be preferably collected from the right upper arm.

As per IFU, participants will have to gently invert the Tasso+™ capillary collection tubes after the full collection process is completed.

4.2.3 *Blood Volume and Clotting Analyses*

Blood volume and clotting analyses will be assessed before centrifugation. Thus, for Cohort B, on Day 1, these endpoints will be assessed by the Site, while for Cohort A, on Day 1 and for Cohorts A and B combined on Days 29 and 57, these endpoints will be assessed by the Central Laboratory (see [Section 6.3](#)).

4.2.4 *Centrifugation*

Tasso+™ blood samples of participants randomized to Cohort A, collected on Day 1, will be centrifuged upon receipt by the Central Laboratory, as per the real-world use of Tasso+™.

Tasso+™ blood samples of participants randomized to Cohort B, collected on Day 1, will be centrifuged and aliquoted by the Site before shipping, following the same procedure as for venipuncture blood samples.

Tasso+™ blood samples of participants from both Cohorts A and B, collected on Days 29 and 57, will be centrifuged upon receipt by the Central Laboratory, as per the real-world use of Tasso+™.

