9.3 Sample Size

Sample size was not calculated on a formal statistical basis; however, Sponsor estimates that the sample size will be sufficient to sample the diversity of user experience regarding the unsupported use of Tasso™ for capillary blood collection.

Each participant will be randomized to either Cohort A or Cohort B in a 2:1 ratio. Thus, it is planned to randomize approximately 133 participants into Cohort A and approximately 67 participants into Cohort B.

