9.5 Efficacy Analyses

9.5.1 Hypothesis Testing Strategy and Multiplicity

Hypothesis testing strategy and multiplicity are not applicable for this study.

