9.5.2 Primary Endpoints

9.5.2.1 Sample Integrity

Descriptive statistics will be presented for the FAS and PPS to summarize the proportion of Tasso+™/SST and Tasso+™/EDTA samples collected on Day 1 for each cohort and on each of Days 29 and 57 for Cohorts A and B combined with the following attributes:

- Adequate volume, defined as at least 300 µL
- Without moderate or gross hemolysis, as defined by Central Laboratory SOP (see Table “Impact of Varying Degrees of Hemolysis” in [Section 6.3.1](#) of the protocol)
- Adequate volume and without moderate or gross hemolysis (for SST samples)
- Without clotting (for EDTA samples only)
- Adequate volume, without moderate or gross hemolysis, and without clotting (for EDTA samples only)

Sample integrity data will be analyzed using the laboratory vendor data for all subjects and visits with the exception of Cohort B Day 1 records, which were collected in the electronic data capture (EDC) system.

Statistical Analysis Plan (SAP)

Protocol: Phase 1 Study Evaluating Technologies for Point-of-Care Blood Collections in Support of Decentralized Outpatient Assessments in Pandemic and Clinical Trial Settings

Version Date: 27-Jun-2025

Sponsor: Resilience Government Services, Inc.

Protocol No: 5309/0024

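### The protocol promises a Day 1 evaluation of centrifugation timing through randomised cohorts, but the SAP plans no estimate of the cohort difference and no measure of its uncertainty

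*Protocol*

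**What the plan says.** Under Protocol 1.2, "The impact of the timing of centrifugation after blood collection" on sample integrity and accuracy is to be evaluated on Day 1. It then describes the two cohorts as the way this will be done: Tasso+ tubes are centrifuged after shipment in Cohort A and at the Site before shipment in Cohort B. Allocation is random (Protocol 4.1): "On Day 1, each participant will be randomized 2:1 to either Cohort A or Cohort B". Under Protocol 4.2.4 the cohorts are handled alike on Days 29 and 57, so Day 1 processing is the only thing that allocation changes.

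The planned analyses stay within cohort:

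- **Integrity (SAP 9.5.2.1).** "Descriptive statistics will be presented for the FAS and PPS to summarize the proportion of" samples meeting each criterion, by cohort on Day 1 and pooled on Days 29 and 57.
- **Accuracy (SAP 9.5.2.2).** Pearson and contingency coefficients between venous and Tasso+ results, for each cohort.
- **Exploratory accuracy (SAP 9.5.4.3).** A contingency coefficient by cohort and transit-time stratum.
- **General statistics (Protocol 9.1, SAP 9.0).** Counts, percentages and the usual continuous summaries. Confidence intervals are not listed.
- **Testing (SAP 9.5.1).** "Hypothesis testing strategy and multiplicity are not applicable for this study".

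On size, Protocol 9.3 says "Sample size was not calculated on a formal statistical basis" and "it is planned to randomize approximately 133 participants into Cohort A and approximately 67 participants into Cohort B".

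**The concern.** A promise to evaluate the impact of a randomised handling step is a promise about a contrast. Two percentages printed side by side leave the reader to do the subtraction and to guess how far the result can be trusted.

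The sample size rests on diversity of user experience and not on the cohort comparison. Nothing else in the documents therefore says what 133 and 67 participants can resolve. A reader could take a chance gap for a processing effect, or take similar figures as evidence that delay does no harm when the data still allow a material difference.

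For accuracy there is a further problem. Pearson's coefficient does not change if every Cohort A result moves by a constant. Setting the two cohort coefficients side by side could therefore miss a systematic shift from delayed centrifugation.

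**Working it through.** **Inputs from the documents.** About 200 participants, allocated 2:1 (Protocol 4.1, 9.3). Rates of 70.0% and 94.5%, from two studies cited in Protocol 1.2, are used only to set a plausible range.

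**Assumptions.** 95% two-sided intervals; one evaluable sample per participant and tube type; the same true rate in both cohorts for the half-widths; illustrative correlations.

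**1. The plan's own figure.** 200 × 2/3 = 133.3 and 200 × 1/3 = 66.7, so the 133/67 split reproduces. The total of 200 cannot be re-derived, because no effect size, power or precision target is stated.

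**2. Difference in integrity percentages.** Half-width = 1.96 × √[p(1−p)(1/133 + 1/67)], with 1/133 + 1/67 = 0.02244.

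| Assumed p | A alone | B alone | A minus B |
|---|---|---|---|
| 70% | ±7.8 | ±11.0 | ±13.5 |
| 80% | ±6.8 | ±9.6 | ±11.7 |
| 90% | ±5.1 | ±7.2 | ±8.8 |
| 94.5% | ±3.9 | ±5.5 | ±6.7 |

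(percentage points)

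If only 70% of samples were evaluable (assumption), the A-minus-B half-width would be ±10.5 at 90% and ±16.1 at 70%.

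**3. What the added line would look like (Newcombe intervals, invented counts).**

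- 93/133 (69.9%) against 57/67 (85.1%): difference −15.1 points, 95% CI −25.7 to −2.5.
- 113/133 (85.0%) against 57/67 (85.1%): 95% CI −9.8 to +11.5. Near-identical percentages would still leave a gap of about 10 points open in either direction.

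**4. Correlations.** By Fisher's z, an observed r of 0.90 has a 95% CI of 0.862 to 0.928 at n = 133 and 0.842 to 0.938 at n = 67. The difference in z has SE √(1/130 + 1/64) = 0.153 and half-width 0.299. With r = 0.95 in one cohort, the other must fall below about 0.911 before the interval excludes zero.

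**5. Mean paired difference.** The half-width of the cohort difference in mean Tasso+ minus venous result is 1.96 × √0.02244 = 0.29 SD of the paired difference, if all pairs are evaluable.

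**6. Which components isolate timing.** Protocol 4.2.3 says of volume and clotting that "for Cohort B, on Day 1, these endpoints will be assessed by the Site", while Cohort A's are read by the Central Laboratory. SAP 9.5.2.1 takes Cohort B Day 1 integrity records from EDC and all others from laboratory vendor data. Protocol 4.2.6 gives the hemolytic index to the Central Laboratory without distinguishing cohorts. So for SST one of two components, and for EDTA two of three, differ by assessor as well as by timing. Hemolysis does not.

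**The case against.** The strongest reply is that this is a descriptive Phase 1 study and the SAP does what the endpoints ask. Centrifugation timing is not among the objectives in Protocol 2.1 to 2.3. The primary endpoints are worded per cohort and not as a contrast, so no listed endpoint goes unanalysed. That stands, and it limits the point to a gap between the rationale and the analysis. It does not remove the gap, since Protocol 1.2 says the evaluation will be made, and an interval requires neither a test nor more participants.

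Some stronger readings are tempting, and the documents do not support them:

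- **That the randomised question gets no quantified answer.** Per-cohort percentages and coefficients are planned, and SAP 9.5.4.5 adds Day 1 volume boxplots by cohort. The point difference in percentages follows by subtraction. What is absent is a planned estimate of the difference and its uncertainty.
- **That the cohort comparison of integrity is unconfounded.** Assessor and data source differ by cohort for volume and clotting, and the study is open-label. An interval measures chance only, so an unqualified interval on the composite would give false assurance.
- **That a cohort contrast in device failures is missing.** Failures arise at collection, before centrifugation, and the endpoint is not reported by cohort.
- **That the SAP gives the absence of tests as its reason for having no estimates.** Section 9.5.1 says only that testing and multiplicity do not apply.

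Randomisation also does not fully protect the analyte contrasts. Protocol Table 5 has moderate hemolysis invalidating potassium and phosphate, so evaluable pairs may differ between cohorts.

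**Conclusion.** The point holds as a gap in estimation. The protocol says the impact of centrifugation timing will be evaluated on Day 1 through randomised cohorts, and neither document plans an estimate of the cohort difference or any interval. At the planned sizes, with all samples evaluable and a common true rate between 70% and 94.5%, observed gaps of roughly 7 to 13 points in an integrity percentage are compatible with chance, and more if samples are lost. The planned summaries remain valid in themselves, so this is an improvement the plan should make and not a defect that invalidates it.

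Reliability is a separate and smaller matter. The planned uses number 200 × 3 × 2 = 1,200, six per person. At an assumed 7% failure rate, a naive interval would be ±1.4 points. Allowing for an assumed within-person correlation of 0.1 to 0.3 (variance × 1.5 to 2.5, from 1 + 5 × ICC), it would be ±1.8 to ±2.3 points.

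**What to change.** Add to SAP 9.5.2, as estimation only and without p-values:

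1. **Lead integrity contrast.** The Day 1 A-minus-B difference in the percentage of samples with a hemolytic index below 2.0, for SST and for EDTA, with Newcombe 95% CIs. State that the Cohort B Day 1 hemolytic index is taken from laboratory data, because the EDC exception in 9.5.2.1 is worded for integrity records as a whole.
2. **Composite integrity difference.** The same for the SST and EDTA composites, with a footnote that Cohort B volume and clotting are read by the Site and Cohort A's by the Central Laboratory, so the difference mixes timing with assessor.
3. **Accuracy.** For each chemistry analyte, the cohort difference in mean paired (Tasso+ minus venous) difference with 95% CI, and the number of evaluable pairs in each cohort. Add Fisher-z CIs for each Pearson correlation.
4. **Primary percentages.** 95% CIs (Wilson or exact) for each integrity percentage.
5. **Reliability, separately.** A participant-clustered 95% CI on the overall failure percentage, with no cohort contrast.

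Site stratification should not be required. No site-stratified randomisation is described, and with up to five sites Cohort B would average only about 67/5 ≈ 13 per site.

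The cost is SAP wording and programming, with no new data. There are 2 + 2 + 9 = 13 contrasts, or 26 if shown in both FAS and PPS, so the tables grow and some differences will be visibly imprecise. The intervals are unadjusted for multiplicity and should be labelled as descriptive.

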1.3 Benefit/Risk Assessment

Risks to study participants include pain, tenderness, redness, swelling, bruising, and persistent bleeding at the puncture site, as well as dizziness, and fainting, that is also occasionally experienced with venipuncture. There is also a slight risk of infection and scarring.

Additionally, collection of upper respiratory fluid using a nasopharyngeal swab for the SARS-CoV-2 polymerase chain reaction (PCR) test may cause discomfort.

Study participants will self-collect blood using the Tasso+™ following appropriate training/instructions (including remote support from a proctor) to complete the administration successfully while minimizing any potential risks associated with the use of Tasso+™ device. Contact information will be provided to each participant in the event they have concerns or need help while using the Tasso+™ device.

There are no direct benefits to participants in this study. However, information collected from this study may be used to improve remote testing and/or diagnostics and to develop telemedicine, thus benefiting ill patients during future pandemics and study participants enrolled in DCTs.

Sponsor Name: Resilience Government Services, Inc., [name]

Protocol Number: 5309/0024

Protocol Version and Date: Version 3.0 – 17 Jan 2025

Page 26 of 75

In conclusion, considering the measures planned to minimize risks to study participants, any potential risks associated with the use of the Tasso+™ device are justified by the anticipated benefits afforded by telemedicine.

